## 9.4.1 Sample size selection

Assuming that the SDAI remission rate is 30% for both ARM-2 and ARM-3, and the noninferiority margin is -15%, the number of subjects required for the lower bound of a twotailed 90% confidence interval for the intergroup difference in SDAI remission rate to exceed the non-inferiority margin at 80% power of detection would be 220 subjects in total (110 in each group).

Past reports suggest that the remission rate of MTX monotherapy is about 15%. Also, it has been reported that about 10% of patients cannot continuously receive MTX  $\geq$ 10 mg/week (Atsumi T, et al. 2016: 75-83). Thus, in order to randomize 220 subjects between ARM-2 and ARM-3, 288 subjects need to be enrolled, and considering some dropouts, a sample size of 300 subjects was selected as the target number of subjects to be enrolled.

<Justification for the estimated SDAI remission rate in ADA/MTX-Reduced Dose Group (ARM-3)>

The estimated SDAI remission rate in ARM-3 was calculated in reference to the results of the MTX Monotherapy  $\rightarrow$  ADA+MTX Group in HOPEFUL 1 Study in which Japanese MTX naïve patients receiving ADA+MTX or MTX alone for 26 weeks, and then, all subjects receiving ADA+MTX for another 26 weeks (Takeuchi T, et al. 2014: 536-43). Since the maximum dosage of MTX in HOPEFUL 1 Study was 8 mg/week (6.6±0.8 mg/week: Mean±SD), the results cannot be directly extrapolated to this study in which the maximum dosage of MTX up to Week 24 will be 16 mg/week; yet, the results would be appropriate to use as a reference for the SDAI remission rate in ARM-3 in which the dosage of MTX will be reduced to 6 to 8 mg/week from Week 24 onward. ARM-3 is designed for patients who have not achieved to SDAI remission at Week 24; thus, assuming that the subjects with SDAI remission at Week 26 in HOPEFUL 1 Study (20 subjects = 163 subjects × 12%) remain to be remission at Week 52, the Week-52 SDAI remission rate among the subjects with SDAI non-remission at Week 26 was calculated to be 31.5% [45/143 subjects, that is (65 subjects - 20 subjects)/(163 subjects -20 subjects)]. Therefore, the SDAI remission rate in ARM-3 was assumed to be 30%.

<Justification for the estimated SDAI remission rate of  $\leq$ 3.3 in ARM-2 (ADA/MTX-MTD Group)>

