2.6. Significance and Confidence Levels

The analysis on non-inferiority will be performed with a two-tailed confidence interval of 90%. A two-tailed significance level of 5% with a two-tailed 95% confidence interval will be used for all other analyses unless specified otherwise.

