2.8. Multiplicity Adjustment

Multiplicity will not be adjusted in this study.

3. Statistical Analysis Set

- 3.1. Definition of Statistical Analysis Set
- 3.1.1. Full analysis set (FAS)

FAS is defined as a group of subjects who receive study drug (MTX) and have evaluable efficacy data at 1 or more time points following the administration of study drug (including subjects who discontinued the study before Week 24 as well as those randomized to ARM-1, 2 or 3).

Modified FAS (mFAS) is defined as a group of subjects who are randomized after Week 24, receive study drug (ADA), and have evaluable efficacy endpoint at 1 or more time points following the administration of study drug (only the subjects randomized to ARM-2 or 3).

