7.2. Analysis Plan of Clinical Laboratory Values and Vital Signs

For continuous variables, descriptive statistics of measurements at each assessment timepoint and their changes from baseline will be calculated for each ARM (ARM-1, 2, and 3). Furthermore, analysis of covariance (ANCOVA) adjusted by country will be performed to make a comparison between ARM-2 and ARM-3, and calculate the estimate of difference between the treatment arms and its two-tailed 95% confidence interval. In addition, descriptive statistics will be calculated, being stratified by country.

As an order categorical variable, clinical laboratory values will be categorized to Lower than the reference (L), Within the reference (N), and Higher than the reference (H), and then the number and proportion of subjects by L, N, and H will be presented in a shift table (baseline vs. each visit during treatment) for each ARM (ARM-1, 2, and 3). In addition, the maximum and minimum values after the start of treatment will be presented in a shift table for comparison with baseline. Furthermore, Wilcoxon rank sum test will be performed to make a comparison between ARM-2 and ARM-3.

Descriptive statistics of vital signs (diastolic blood pressure, systolic blood pressure, pulse rate, body temperature) and body weight at each assessment timepoint and their changes from baseline will be computed for each ARM (ARM-1, 2, and 3). Furthermore, analysis of covariance (ANCOVA) adjusted by country will be performed to make a comparison between ARM-2 and ARM-3, and calculate the estimate of difference between the treatment arms and its two-tailed 95% confidence interval.

8. Analysis Plan of Exploratory Endpoints

8.1. Erythrocyte MTX-PG Concentration at Weeks 0, 4, 8, 12, 24, 36, and 48 Descriptive statistics for erythrocyte MTX-PG concentrations as well as change from baseline and change rate from baseline will be calculated by country. In addition, descriptive statistics for Week 24 onward will be calculated at each assessment timepoint for each ARM (ARM-1, 2, and 3).

Pearson's product-moment correlation coefficient, Spearman's rank correlation coefficient, and their 95% confidence interval will be calculated at each assessment timepoint to evaluate the correlation of exposure to MTX, SDAI, mTSS, and ACR-N to erythrocyte MTX-PG concentration. Furthermore, cutoff values for AST increased, ALT increased, and WBC decreased, and their differences among the participating countries will be discussed.

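### SAP 7.2 compares laboratory categories between ARM-2 and ARM-3 on a single Low–Normal–High rank scale and does not say which values are tested; separate low and high risk differences should be added

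*SAP*

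**What the plan says.** SAP 7.2 plans the following for laboratory data:

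- Descriptive statistics and a country-adjusted ANCOVA of continuous values, ARM-2 against ARM-3.
- Categories, treated as one ordered variable: "Lower than the reference (L), Within the reference (N), and Higher than the reference (H"), shown by arm as a shift from baseline at each visit.
- Shift tables of the lowest and highest value after treatment starts.
- Directly after these: "Furthermore, Wilcoxon rank sum test will be performed to make a comparison between ARM-2 and ARM-3".

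The last sentence does not name the variable ranked. It could be the category at a visit, the category of the minimum or maximum, or the shift. No between-arm comparison of low values alone or high values alone is specified. Protocol 9.2.3.2 has the shift tables but no between-arm laboratory test.

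Elsewhere the SAP does attach a direction to laboratory harm: section 8.1 will discuss "cutoff values for AST increased, ALT increased, and WBC decreased". On error rates, SAP 2.6 says "A two-tailed significance level of 5% with a two-tailed 95% confidence interval will be used for all other analyses", and SAP 2.8 says "Multiplicity will not be adjusted in this study".

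**The concern.** A rank test on L < N < H asks whether one arm sits higher on the scale overall. Laboratory harm usually lies in one tail of a given parameter. Three things follow if visit categories are ranked:

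1. High values that are equally common in both arms add variability and dilute a difference in low values.
2. If low and high values of the same parameter both become more frequent in the same arm, the two movements offset each other.
3. A small p-value does not show whether it came from the low tail, the high tail or both.

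Protocol 3.3 expects a lower MTX dose to reduce dose-dependent reactions, so the laboratory comparison of the two randomised arms has some weight as safety evidence. The risk is that a non-significant result printed beside the shift tables is read as no difference, or that a significant one is read as toxicity when it reflects the other tail.

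**Working it through.** The SAP gives no figure for this test, so there is none to reproduce. The check asks what the test measures and how its power compares with a test on low values only.

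**Inputs.** Arm size: Protocol 9.4.1, "would be 220 subjects in total (110 in each group"). Two-sided 5% level: SAP 2.6. All L/N/H rates are assumptions, because the documents give none; a range is shown.

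**Step 1: what the test measures.** With category probabilities L₁, N₁, H₁ in ARM-2 and L₂, N₂, H₂ in ARM-3, the test responds to δ = P(ARM-2 lower) − P(ARM-2 higher), which works out as

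δ = (L₁ − L₂) − (H₁ − H₂) − L₁H₂ + H₁L₂.

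An excess of high values in an arm is subtracted from its excess of low values.

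- Low 15% v 4%, High 10% in both: 0.11 − 0 − 0.015 + 0.004 = 0.099.
- Low 15% v 4%, High 15% v 4%: 0.11 − 0.11 − 0.006 + 0.006 = 0.

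**Step 2: why equal high rates cost power.** The rank-sum variance is V = (n₁n₂/12)[(N+1) − Σ(t³ − t)/(N(N−1))], where t are the pooled category counts, and the expected z is (n₁n₂δ/2)/√V. Here n₁n₂ = 12,100, N = 220 and N(N−1) = 48,180.

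- No high values (t = 20.9, 199.1, 0): bracket 221 − 164.0 = 57.0; √V = √(1008.3 × 57.0) ≈ 240; z = 12,100 × 0.110/2/240 ≈ 2.8.
- High 10% in both (t = 20.9, 177.1, 22): bracket 221 − 115.7 = 105.3; √V ≈ 326; z = 12,100 × 0.099/2/326 ≈ 1.8.

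The low excess is the same 11 points in both, but z drops from above to below 1.96.

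**Step 3: power by simulation** (tie-corrected Wilcoxon on the three categories; Fisher's exact test on Low against the rest; 110 per arm).

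| ARM-2 L/N/H % | ARM-3 L/N/H % | δ | Wilcoxon | Fisher on Low |
|---|---|---|---|---|
| 15/85/0 | 4/96/0 | 0.110 | 83% | 76% |
| 15/81/4 | 4/92/4 | 0.106 | 64% | 76% |
| 15/75/10 | 4/86/10 | 0.099 | 45% | 76% |
| 15/75/10 | 4/90/6 | 0.065 | 24% | 76% |
| 15/70/15 | 4/92/4 | 0 | 6% | 76% |
| 15/81/4 | 4/88/8 | 0.140 | 83% | 76% |
| 5/90/5 | 5/72/23 | 0.171 | 91% | 2% |

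Rows 1 to 3 show dilution, rows 4 and 5 cancelling. Row 6 is a case where the planned test does better. In row 7 low values do not differ at all, yet the Wilcoxon test is nearly always significant.

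**Step 4: worked examples.**

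- Counts 22/66/22 v 5/100/5. Pooled midranks are 14, 110.5 and 207. The ARM-2 rank sum is 22×14 + 66×110.5 + 22×207 = 12,155; its expectation is 110×221/2 = 12,155. So z = 0 and p = 1.00. Yet low values are 20.0% v 4.5%: difference 15.5 points (95% CI 7.0 to 23.9), Fisher p = 0.0007.
- Counts 22/83/5 v 5/100/5, the same low excess without a high excess. Midranks are 14, 119 and 215.5, the rank sum is 308 + 9,877 + 1,077.5 = 11,262.5, z = −2.91 and p = 0.004. The planned test finds it.

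**Step 5: dependence on the input.** The table applies to a single category per subject in which L and H both occur, as at one visit. If the test were run on the category of each subject's minimum, high values would be fewer and cancelling much reduced. It need not vanish: Protocol 7.5 schedules hematology and chemistry at only Weeks 36 and 48 after Week 24, so a subject high at both would still rank as H.

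**The case against.** The strongest reply is that the damaging pattern is hypothetical. Cancelling needs more low and more high values of the same parameter in the same arm, and no section gives rates suggesting this. The blood-count harms the documents name are decreases: bone marrow depression (Protocol 2.4.2 and 7.4.1), the cytopenias listed for ADA (7.4.1) and the fall in WBC in SAP 8.1. A plain excess of low values is usually found (row 1 and the second example), and the planned test sometimes beats Fisher's (rows 1 and 6). The Wilcoxon sentence also directly follows the one on minimum and maximum values, so it may be meant for those.

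Most of this stands. An inference the other way is possible: Protocol 2.3.2 reports more infection at MTX of 10 mg/week or above, and infection can raise the white count while MTX depresses it. That is plausible, not documented. Dilution by background high values needs no such pattern, though its size also rests on assumed rates.

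A reader might go further and infer that the plan would let real blood-count toxicity go unseen. The documents do not support that. SAP 7.2 shows L, N and H counts by arm and tabulates minimum and maximum values, and SAP 7.1 tabulates adverse events by arm and compares drug-related events at Weeks 24 to 48 by Fisher's exact test.

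Those outputs are nevertheless not a substitute for a suitable laboratory comparison. The shift tables are descriptive. ANCOVA compares means, which can offset in the same way. Under Protocol 8.1.1 a laboratory change is an adverse event only if it leads to discontinuation, needs intervention or is so judged by the investigator. The Fisher test depends on causality judgements in an open-label trial.

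**Conclusion.** The point holds as a minor one. The between-arm laboratory test has an undefined input and, if it ranks visit categories, answers a net-shift question rather than a question about either tail. For an 11-point excess of low values at 110 per arm, its power runs from 83% with no high values to 64% with 4% and about 45% with 10% high in both arms, against about 76% for a test on low values. It falls to about 6% only under complete cancelling, for which the documents give no evidence. These figures rest on assumed category rates and on the planned arm size being reached.

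The consequence is confined to the formal laboratory comparison of ARM-2 and ARM-3. No decision rule depends on its p-value, and the non-inferiority analysis of SDAI remission is unaffected. It is also tempting to conclude that the Wilcoxon test should be replaced by one declared toxic direction per parameter. That goes too far: it would discard the other tail, and the documents give no direction for several tests listed in Protocol 7.4, such as MCV, uric acid and IgG.

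**What to change.** In SAP 7.2:

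1. Keep the L/N/H and minimum/maximum shift tables.
2. For each parameter, compare ARM-2 with ARM-3 on the proportion of subjects with any value below the reference after Week 24 (from the minimum over that period) and, separately, any value above it (from the maximum). Report the country-stratified Mantel-Haenszel risk difference with 95% CI, the format already used in SAP 6.2 for binary outcomes, or Fisher's exact test where counts are sparse. The period must be stated, because the planned minimum and maximum run from the start of treatment, which may include the weeks before randomisation.
3. Name the direction of main interest in advance where the SAP already gives one: low for WBC, high for AST and ALT. Report both tails for every parameter.
4. If the Wilcoxon test is kept, call it supplementary and state which variable it ranks.

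**Cost.** A few sentences and minor programming on categories already planned; no new data. The drawback is two comparisons per parameter instead of one. Protocol 7.4 lists 18 items (6 hematology, 11 chemistry, IgG), so at least 36 comparisons. With no multiplicity adjustment, up to about 36 × 0.05 = 1.8 would be nominally significant by chance if the arms did not differ. They are best presented as estimates with intervals, not as a set of tests.

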## 3.3 Purpose

A lower dosage of MTX, which is effective in combination with ADA in MTX-refractory RA patients is expected to reduce MTX-related ADRs that dose-dependently increase.

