## 4.3 Bias

#### 4.3.1 Randomization

If a subject does not achieve to clinical remission (SDAI  $\leq$ 3.3) at Week 24 despite the maintenance of MTX dose at  $\geq$ 10 mg/week, the subject will start receiving ADA as an add-on therapy. Subjects then will be stratified by countries (Japan, South Korea, and Taiwan) as a stratification factor, and for each stratum, subjects will be randomized at a 1:1 ratio to either a group in which the MTD of MTX (10 to 25 mg/week) will be maintained (ARM-2), and a group in which the dosage of MTX will be reduced to 6 to 8 mg/week (ARM-3). Upon completion of Week 24 assessments, principal investigator/sub-investigator shall enter the Week 24 dosage of MTX, tender joint count (28 joints), swollen joint count (28 joints), VAS (physician- and patient-reported; 10 cm scale), and CRP in IWRS. If all necessary information is entered, a relevant treatment group in line with the status of randomization (ARM-1, ARM-2 or ARM-3) will be issued by IWRS.

The MTX dosage shall be either 6 mg/week or 7.5 mg/week in subjects in ARM-3 whose maintenance dose of MTX at Week 24 is 10 mg/week.

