#### 7.5 Assessment schedule

Assessments should be performed in accordance with the following schedule.

Screening period will be within 8 weeks before the start of study treatment. Assessment time points are counted from Week 0, and assessments should be performed within  $\pm 1$  week from each timepoint (Week 4 to 12), and  $\pm 2$  weeks from each timepoint (Week 24 onward).

Assessments	Screening period	Wk 0	Wk 4	Wk 8	Wk 12	Wk 24	Wk 36	Wk 48 or ET
Informed consent	°*1							
Demographics	0							
Eligibility	0							
History of disease/surgery	0							
Concomitant therapy	•							
General symptoms	0	0	0	0	0	0	0	0
Vital signs	(0)	0				0		0
Height, body weight	0					0		0
Physical examinations	0	0	0	0	0	0	0	0
Tender joint count, swollen joint count	0	0	0	0	0	0	0	0
Evaluation using VAS (physician- and patient- reported)	0	0	0	0	0	0	0	0
Assessment using HAQ	(0)	0	0	0	0	0	0	0
12-lead ECG	°*2							
Chest X ray	o*2					0		0
X ray of hands and feet	o*2					0		o *4
Infection disease test	°*3							
Clinical laboratory (hematology, chemistry)	(0)	0	0	0	0	0	0	0
IgG	°*2					0		0
CRP, ESR	0	0	0	0	0	0	0	0
MMP-3, RF	°*2	(0)	(0)	(0)	0	0	0	0
Anti-CCP antibody	o *3							(0)
MTX-PG		0	0	0	0	0	0	0
Cytokine		0				0		0
Micro RNA						0		
Anti-adalimumab antibody						0		0
AEs		•						•

\*1 : The informed consent of the study should be obtained prior to the screening test. However, the data before obtaining the consent may be included in the study if they have been assessed within the designated period.

\*2 : The test results may be used if they were obtained within 12 weeks before consent. Also, the test may be performed at Week 0

\*3 : The test results may be used if they were obtained within 2 years before consent. Also, the test may be performed at Week 0

\*4 : The X rays of the hands and feet is unnecessary to be performed for early termination if early termination occurs within 28 days after the last X-rays.

 $\bigcirc$ : Essential items, ( $\bigcirc$ ): Optional items

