## 9.2.3.1 Adverse events (AEs)

AEs recorded in EDC will be reinterpreted with ICH Medical Dictionary for Regulatory Activities (MedDRA). AEs recorded in EDC will be reinterpreted to the closest MedDRA lowest level terms (LLT) (Ver. 19.0 or later version). Preferred term (PT) and system organ class (SOC) will also be entered in the database. Treatment-emergent adverse events (TEAE) means AEs not confirmed before the study treatment (MTX) and emerges for the first time after the start of study treatment. TEAE also includes:

- Events confirmed before the study treatment which disappears immediately before the start of study treatment, but reemerges during the study treatment; and
- Events confirmed before the study treatment, which becomes severer during the study treatment compared to the level of severity before the start of study treatment.

TEAE will be used for the analysis of AEs. The number (proportion) of subjects with TEAE in each ARM will be tabulated in SOC and PT. Two or more AEs with the same MedDRA term may be reported in a single subject; in such case, the AEs will be interpreted and counted as 1 subject pertinent to the analysis, and also the AE with the highest severity will be counted in for the analysis on the number (proportion) of subjects with the TEAE. Furthermore, the number (proportion) of subjects with TEAE will be tabulated by the presence/absence of causality.

In addition, TEAE for which causality with the study treatment cannot be ruled out (ADR) will be tabulated in terms of SOC and PT, and the AEs with the highest severity will be counted in for the analysis on the number (proportion) of subjects.

The incidence of TEAE that occur from Week 24 to 48 will be compared between ARM-2 and ARM-3 using a Fisher's exact test or other relevant method.

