2.3. Handling of Study Data

- · Fixed data after the completion of follow-up will be used for statistical analyses.
- For subjects who were enrolled more than once, statistical analyses will be conducted by removing the data that became unnecessary.
- Data handling meeting will be held prior to the database lock to discuss and determine how to handle individual data after removing the information on which treatment arm each subject was randomized to.
- For clinical laboratory values that exceed or fall below detection limits, detection limits will be substituted for actual values.
- As a rule, baseline is defined as Week 0. If the value at Week 0 is missing or not measured, the time of screening is regarded as baseline.
- · Change and percentage change are defined as follows:

Change = measured value after intervention – measured value at baseline Percentage change = (change/measured value at baseline) x 100 (%)

- 2.4. Handling of Missing Values
 - Subjects with missing data at an assessment time point of SDAI remission, ACR20, ACR50, and ACR70 response, HAQ remission, and structural remission due to study discontinuation or other relevant reasons will be considered as a "non-responder" at the time point of missing data.
 - Subjects with missing data at an assessment time point of CDAI, DAS28-ESR, DAS28-CRP remission due to study discontinuation or other relevant reasons will be considered as a "non-responder" at the time point of missing data.
 - Any missing data on SDAI, CDAI, DAS28-ESR, and DAS28-CRP will be considered as missing at the time point of missing data.

If there is a missing data on the assessment of SDAI, CDAI, DAS28-ESR, DAS28-CRP, and mTSS, the sensitivity analysis of GEE or MMRM method will be performed. If the result does not converge, a missing data will be imputed with the last observation carried forward (LOCF). In addition, for the sensitivity analysis of primary endpoint, a missing data on the final scheduled visit will be imputed with data on End of Study.

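### The worst-value laboratory table in SAP 7.2 runs from Week 0, so an ARM-2 v ARM-3 reading of it is diluted by visits before randomisation; the data for the Wilcoxon test are not stated

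*SAP*

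**What the plan says.** SAP 7.2 sorts laboratory values into low, normal and high against the reference range and plans two kinds of shift table. The first sets baseline against each visit, by ARM. For the second, "the maximum and minimum values after the start of treatment will be presented in a shift table for comparison with baseline". The paragraph then ends: "Furthermore, Wilcoxon rank sum test will be performed to make a comparison between ARM-2 and ARM-3". It does not say whether the test uses the by-visit categories, the worst-value categories or both, and it names no time window. Protocol 9.2.3.2 plans the same worst-value table but no between-arm test.

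The dates follow from other sections:

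- **Baseline.** SAP 2.3: "As a rule, baseline is defined as Week 0" (screening if Week 0 is missing).
- **Start of treatment.** This is MTX at Week 0, not adalimumab at Week 24. Protocol 6.1 starts MTX after the Week 0 assessments, and Protocol 9.2.3.1 defines treatment-emergent events as "AEs not confirmed before the study treatment (MTX) and emerges for the first time after the start of study treatment".
- **Visits.** In Protocol 7.5, the row that begins "Clinical laboratory (hematology, chemistry" is marked as essential at Week 0 and then at Weeks 4, 8, 12, 24, 36 and 48 or early termination.
- **Randomisation.** Protocol 4.3.1: "Upon completion of Week 24 assessments, principal investigator/sub-investigator shall enter the Week 24 dosage of MTX". The allocation is issued after that entry, so the Week 24 sample precedes randomisation.

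**The concern.** ARM-2 and ARM-3 follow the same regimen until randomisation, including escalation to the maximum tolerable MTX dose. Only values after Week 24 can reflect the dose contrast. A maximum or minimum cannot be undone by later values: a subject whose ALT was high at Week 12 stays in the high category in ARM-3 even if ALT returns to normal on the reduced dose. Here the outcome itself, and not only its reference value, contains data from before randomisation.

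This bears on the trial's purpose. Protocol 3.3 says that a lower MTX dose "is expected to reduce MTX-related ADRs that dose-dependently increase", and Protocol 2.2.1 lists hepatic impairment and myelopathy among the dose-dependent reactions. The trial is open-label. Under Protocol 8.1.1, a laboratory change counts as an adverse event only if it leads to discontinuation, needs intervention or is judged to be one by the investigator. Laboratory values are therefore the safety measure least open to judgement, and dilution would understate a hepatic or haematological advantage of ARM-3 if there is one.

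Elsewhere the SAP does cut at Week 24. Section 7.1 tabulates adverse events by ARM from Week 24 and compares drug-related events for Weeks 24 to 48. Section 6.2.8 compares mTSS change from Week 24 to Week 48, and section 8.1 summarises MTX-PG by ARM from Week 24. Section 7.2 has no such cut.

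**Working it through.** **Visit count.** Post-baseline haematology and chemistry visits are Weeks 4, 8, 12, 24, 36 and 48: six. Those at or before randomisation are Weeks 4, 8, 12 and 24: four. Those after it are Weeks 36 and 48: two. IgG is measured after baseline only at Weeks 24 and 48, so the count does not apply to it.

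**Size of the comparison.** The documents give no figure for the laboratory comparison. Protocol 9.4.1 gives 110 per arm for 80% power on the primary test. With 30% in both arms, a 15-point margin and a two-sided 90% interval, power at 110 is Φ(0.15/√(0.42/110) − 1.645) = Φ(0.783) = 78.3%. That is close enough to take 110 per arm as the planned size; nothing below depends on the gap.

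**Direction of the error.** Let π be the share of subjects already abnormal at some visit up to Week 24, equal in expectation in both arms. Let r2 and r3 be the shares abnormal after it. If the two periods are independent, P(ever abnormal) = π + (1 − π)r, so the difference becomes (1 − π)(r2 − r3). For assumed r2 = 25% and r3 = 10%, the difference is 15 points. With π = 10%, 30% or 50% it falls to 13.5, 10.5 or 7.5 points.

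**Size with correlated visits.** All rates are assumptions. Each subject has a latent normal value at six visits, with correlation 0.6, and is high when it exceeds the visit's threshold. After Week 24 the by-visit rate is 20% in ARM-2 and 8% in ARM-3. Before it, both arms share one of two sets of rates at Weeks 4, 8, 12 and 24:

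- higher: 10%, 15%, 20%, 20% (50-100% of the ARM-2 rate);
- lower: 2%, 4%, 6%, 6% (10-30% of it).

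Power is for two proportions at n = 110 per arm and two-sided 5%: SE = √{[p2(1 − p2) + p3(1 − p3)]/n}, power = Φ(d/SE − 1.96) + Φ(−d/SE − 1.96).

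| Data used | ARM-2 | ARM-3 | Difference | Power |
|---|---|---|---|---|
| Worst of Weeks 36 and 48 | 30% | 13% | 17 points | about 88% |
| Worst of all six, higher early rates | 44% | 38% | 6.5 points | about 17% |
| Worst of all six, lower early rates | 33% | 19% | 14 points | about 65% |
| One visit after randomisation | 20% | 8% | 12 points | about 74% |

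For example, for one visit SE = √[(0.16 + 0.0736)/110] = 0.0461, 0.12/0.0461 = 2.60, and Φ(2.60 − 1.96) = 74%.

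**Sensitivity.** I crossed by-visit rates of 15-25% in ARM-2 with 5-10% in ARM-3 and correlations of 0.3-0.8, with early rates at 50-100% of the ARM-2 rate. The difference on Weeks 36-48 ranges from about 6 to 31 points, and on all six visits from about 3 to 11. It shrinks in every case. At 15% v 10%, even the Weeks 36-48 window has only about 24-31% power.

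**The case against.** The strongest reply is that the SAP never says the Wilcoxon test uses the worst-value table. The paragraph is about ordered categories in general, the by-visit table comes first, and the worst-value table is an addition. If the test is by visit, the worst-value table only describes whole-study exposure. Testing one post-randomisation visit would then cost only the step from about 88% to about 74% power in the example. This stands: the link between test and table is the natural reading of the sentence order but is not stated. A by-visit test would still have no named visit.

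A reader might also infer that the plan conceals a difference in liver or blood toxicity. The documents do not support that. The same section plans by-visit shift tables and descriptive statistics by ARM, so Weeks 36 and 48 appear on their own. SAP 7.1 compares drug-related events over Weeks 24 to 48.

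The size can be disputed too. Early abnormality among randomised subjects may be low, because Protocol 5.3 withdraws those who cannot hold MTX at 10 mg/week or more at Week 24. The calculation models any high value, not the three ordered categories that a Wilcoxon test would use. Finally, this is a supportive safety table with no success criterion, and dilution does not by itself create an apparent benefit for ARM-3. These points limit the weight of the finding but do not justify the window.

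**Conclusion.** The point holds for one table and for any test attached to it. For haematology and chemistry, four of the six visits behind the worst value precede randomisation, so an ARM-2 v ARM-3 comparison of that table is diluted toward no difference. The visit count and the direction follow from the documents. The size does not, because they give no abnormality rates: in the illustration, power falls from about 88% to about 17% with high early rates, but only to about 65% with low ones. Separately, the Wilcoxon test has no defined data or window, and that needs settling whichever table was meant. The by-visit and Week 24-48 analyses remain valid, so this is an inexpensive improvement to a supportive analysis and not a flaw in the trial's safety assessment as a whole.

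**What to change.** In SAP 7.2, for ARM-2 v ARM-3:

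1. Take the maximum and minimum over values after randomisation only: Weeks 36 and 48 or early termination, plus any unscheduled values in the EDC.
2. Build the shift table from the Week 24 category instead of the Week 0 category.
3. Name this table as the data for the Wilcoxon test. If a by-visit test is also wanted, name the visit.
4. Keep the table from Week 0 as a description of exposure over the whole study, with no between-arm test.

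The cost is a few lines of SAP text and one table specification, with no new data. The drawback is that the worst value then rests on two scheduled visits instead of six, but these are the only two scheduled visits that can reflect the randomised dose contrast. If the true difference is small, as in the 15% v 10% case, the comparison will still have low power.
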